5.1 Sample Size Determination

The proposed study was powered based on consideration of multiple effect size calculations from a single bout of HIIT vs MICT in young men ($F=0.25-0.99$)(16) on markers of carbohydrate oxidation, glucose, citric acid, and succinate acid. To achieve statistical power of 0.80, with a conservative correlation of 0.5 between repeated outcomes, the estimated sample size required was $N=12$. To account for an 18% dropout/disqualification rate and for equal groups we propose to enroll 14 adults with T1D, with an equal sample of men ($n=7$) and women ($n=7$).

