Statistical Methodology	
Aim 1: Principal Component Analysis for metabolomics data; two-way ANOVA [regimen (HIIT vs. MICT vs. CON) \times time (base vs. immediate post vs. 1h post)]
 
Aim 2: Two-way mixed-factorial ANOVA for counterregulatory hormones; Comparison of area under the curve across all trials for CGM, aggregated over 24 hrs
 
Aim 3: Spearman correlations between metabolomic outcome and physiological variables)

Abbreviations and Definition of Terms

Abbreviations and Definitions of Terms	
Abbreviation:	Formal Title:
HIIT	High Intensity Interval Training
MICT	Moderate Intensity Continuous Training
T1D	Type 1 Diabetes
CON	Control (no exercise)
CGM	Continuous Glucose Monitoring
HbA1c	Hemoglobin A1c
VO ₂ peak	Peak Oxygen Consumption
PAR-Q+	Physical Activity Readiness Questionnaire
BMI	Body Mass Index
4C Model	Four Compartment Model
FM	Fat Mass
%fat	Percent Body Fat
LM	Lean Mass
DXA	Dual-energy x-ray Absorptiometry Total Body Scan
BIS	Bioelectrical Impedance Spectroscopy
VT	Ventilatory Threshold
HR	Heart Rate
HR _{max}	Maximal Heart Rate
TIR	Time-in-Range
CHO	Carbohydrate
PRO	Protein
FAT	Fat
NDSR	Nutrient Data System for Research
ELISA	Enzyme-Linked Immunosorbent Assay
MVPA	Moderate-Vigorous Physical Activity
EDTA	Ethylenediaminetetraacetic acid
W	Watts
EXSS-IRB SOP	Exercise and Sport Science Institutional Review Board Standard Operating Procedures
DAIDS	Division of AIDS
AE/SAE	Adverse Event/Serious Adverse Event
UPIRSO	Unanticipated Problems Involving Risks to Subjects or Others
DSMB	Data and Safety Monitoring Board
APL	Applied Physiology Laboratory

1 Introduction

This document is a protocol for a human research study. This study will be conducted according to US and international standards of Good Clinical Practice (FDA Title 21 part 312 and International Conference on Harmonization guidelines), applicable government regulations and Institutional research policies and procedures.

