Specific Aim 1: To compare the metabolic responses immediately and 1 hr after HIIT compared to MICT matched for total energy expenditure, vs no exercise in 14 adults with T1D. Metabolism will be defined as energy expenditure (via indirect calorimetry), carbohydrate metabolism (tricarboxylic acid intermediates), and fat metabolism (acylcarnitines, respiratory exchange ratio).

Specific Aim 2: To evaluate key counter-regulatory/metabolic hormones (i.e. cortisol, lactate, glucagon, and insulin) during and after HIIT, MICT, and control (CON) sessions and the change in glycemia (using continuous glucose monitoring and glycemic cutpoints [<70 mg/dL, 70 - 180 mg/dL, >180 mg/dL]) for 48 hrs post exercise.

[figure not shown]
Specific Aim 3: To explore the modulatory effect of physiological variables on metabolism, including biological sex, lean body mass and visceral fat (measured from dual energy x-ray absorptiometry). Body fat percentage, lean mass, and visceral fat will be used to characterize the sample; the relationship of these variables with metabolomic intermediates will be assessed.

3 Study Design

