Approximately 8 mL of blood sample (~ 1.5 teaspoons) using an EDTA tube will be taken upon arrival, immediately after exercise, and one-hour post exercise. CON intervention visit will consist of a single blood draw. Circulating metabolites will be measured using an untargeted mass spectrometry-based platform with fasting concentrations of up to 1500 endogenous metabolites related to mitochondrial function, fatty acid oxidation, insulin resistance, and glucose regulation. Analysis will be completed at the Duke Molecular and Physiology Institute Metabolomics Core, directed by [name]. Targeted metabolomics analysis for acylcarnitines and amino acids will be completed; non-targeted analyses will also be performed, in order to promote the identification of unknown metabolites in addition to the known biology and physiology. Counterregulatory hormones (cortisol, lactate, glucagon) and insulin will be analyzed. Samples will be centrifuged immediately upon collection, and aliquots of plasma will be immediately frozen at -80° C for batch analysis. All blood draws will be done in the Applied Physiology Lab by an individual trained in phlebotomy. The current lab group has previously received approval for intravenous blood draws from the antecubital region in several IRB#, to name a few: 16-1991, 15-0543, and 14-0777, with no adverse events reported.

Treatment Regimens: (~20- 30 minutes)

- 1) HIIT Intervention: A 2 minute self-selected warm-up, followed by 10 alternating sets of one minute of pedaling at a resistance corresponding to 90% of VO₂peak and one-minute in active recovery at 50 watts (W). The work completed during each interval will be calculated by multiplying the power output for each participant at 90% VO₂peak by the duration of the interval (60 s). The work completed during each recovery period will be added by multiplying the power output (50 W) by the duration of the recovery period (60 s). The work from both bouts will be added together and then multiplied by 10 to calculate the total amount of work that each participant will complete in the HIIT trial.
- 2) MICT Intervention: Subjects will cycle continuously at a workload corresponding to 65% VO₂peak (W) for a pre-calculated length of time (~20-30 minutes), equivalent to the work that will be completed in the HIIT trials.
- 3) CON Intervention: No exercise will be performed. Subjects will arrive to the lab following the same pre-testing guidelines followed for HIIT and MICT trials.

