5.2 Statistical Methods

For aim 1, changes in the first principal component, as well as any additional components for which the associated eigenvalue is greater than one, will be evaluated using paired t-tests at the 2-sided 0.05 level. Changes in individual metabolic intermediates will be evaluated using paired t-tests at the 2-sided 0.01 level. Differences in metabolomics and counterregulatory hormones markers between treatment regimens will be evaluated using two-way ANOVAs [regimen (HIIT vs. MICT vs. CON) \times time (base vs. immediate post vs. 1h post)]. Exploratory analysis of the modulatory effects of sex on metabolomics markers will be evaluated using separate regimen-by-sex mixed factorial ANOVAs [regimen \times sex], at each time point.

For aim 2, CGM data will be evaluated as previously recommended; data will be aggregated over the 24hrs; area under the curve data will be compared across trials.(25) Counter-regulatory hormones will be evaluated using a two-way mixed factorial ANOVA. Activity data will be captured to potentially be used as a covariate when collating CGM data.

For aim 3, spearman correlations will be completed to understand associations between metabolomics outcomes and physiological variables (i.e. body fat, lean mass, visceral fat).

6 Safety and Adverse Events

Risks associated with participating in this study are **possible**. In-test monitoring by the research team, who are certified fitness professionals trained in CPR/AED, are in place to ensure the safety of all subjects. Personnel trained in phlebotomy and with radiation exposure training will complete the blood draws and DXA scans, respectively.

In accordance with the Exercise and Sport Science Institutional Review Board Standard Operating Procedures (EXSS-IRB SOP), 3 trained research personnel (for safety purposes per IRB procedures) will perform cardiorespiratory fitness testing. Other precautions include: licensed medical professional (MD, ATC) on call, operational AED, and a land line within 10 feet of the testing in order to make emergency call, if required. Additionally, the lab is located within 500 feet of the University Athletic Training facility. If a cardiovascular event does occur, 911 will be called; UNC Hospitals and Emergency room are in very close proximity to the lab.

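### One CON blood draw cannot supply the regimen x time ANOVA planned for metabolites and hormones; separately, enrolling 14 does not quite cover 18% loss on N=12

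*Combined protocol and SAP*

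**What the plan says.** On CON sampling, the sections disagree.

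- Section 4.1, Metabolomics: three draws at an exercise visit (arrival, directly after exercise, one hour later), but "CON intervention visit will consist of a single blood draw". The time of that draw is not given.
- Section 5.2: "Differences in metabolomics and counterregulatory hormones markers between treatment regimens will be evaluated using two-way ANOVAs", with three regimens (HIIT, MICT, CON) crossed with three times (base, immediate post, 1 h post). The Study Summary gives the same model for Aim 1. Section 5.2 adds: "Exploratory analysis of the modulatory effects of sex on metabolomics markers will be evaluated using separate regimen-by-sex mixed factorial ANOVAs", one at every time point.
- Section 2, Specific Aim 1: "To compare the metabolic responses immediately and 1 hr after HIIT compared to MICT matched for total energy expenditure, vs no exercise".
- Section 3.2: circulating metabolites are the primary outcome, sampled at three times. Section 3.2a puts the hormones at the same times.
- Section 4.1, Visit 3-5: the procedures are the same at all three visits, apart from the absence of exercise on CON.

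On sample size, section 5.1 says: "The proposed study was powered based on consideration of multiple effect size calculations from a single bout of HIIT vs MICT in young men", with F from 0.25 to 0.99. It continues: "To achieve statistical power of 0.80, with a conservative correlation of 0.5 between repeated outcomes, the estimated sample size required was" 12. Then: "To account for an 18% dropout/disqualification rate and for equal groups we propose to enroll 14 adults with T1D", seven men and seven women. It does not state the test, the alpha or the single effect size used.

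**The concern.** The CON arm is there to show what the blood markers do over the same period without exercise. If only one CON sample is taken, the planned model has cells that no participant can fill. That is absence by design, so no missing-data method recovers it. Staff who follow the Metabolomics paragraph literally would take one sample, and samples not taken cannot be recovered afterwards. What is at stake is the no-exercise contrast for the primary outcome and for the hormones.

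The second matter is smaller. Section 5.1 presents 14 as covering an 18% loss from a requirement of 12, and the arithmetic falls short. Because the basis of the 12 is not given, a reader cannot tell what power remains if 11 complete.

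**Working it through.** **1. Cells available with one CON draw.** The table takes the draw to be on arrival, which is an assumption.

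| | Base | Immediate post | 1 h post |
|---|---|---|---|
| HIIT | yes | yes | yes |
| MICT | yes | yes | yes |
| CON | yes | none | none |

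Moving the single draw to another time moves the two empty cells but does not fill them.

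Interaction degrees of freedom are filled cells minus additive parameters (1 + 2 + 2 = 5). With nine cells: 9 - 5 = 4. With seven: 7 - 5 = 2. The lone CON cell is used up in estimating the CON main effect, so both remaining degrees of freedom compare HIIT with MICT over time. Change over time within CON needs at least two CON samples and cannot be estimated. The regimen x sex ANOVAs have no CON data at two of their three times.

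The paired t-tests of change within HIIT and within MICT (section 5.2) use no CON sample and are unaffected.

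**2. Reproducing N=12.** Inputs from section 5.1: power 0.80, correlation 0.5, f between 0.25 and 0.99 (reading F as Cohen's f). Assumed: alpha 0.05 and sphericity. Noncentral F with lambda = f^2 x N x cells / (1 - 0.5) and df2 = df1 x (N - 1).

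| Test | f | lambda at 12 | df at 12 | Power at 11 | Power at 12 |
|---|---|---|---|---|---|
| 3x3 interaction | 0.25 | 0.0625 x 12 x 9 / 0.5 = 13.5 | 4, 44 | 0.762 | 0.807 |
| One factor, three levels | 0.40 | 0.16 x 12 x 3 / 0.5 = 11.52 | 2, 22 | 0.773 | 0.816 |
| HIIT vs MICT, two levels | 0.45 | 0.2025 x 12 x 2 / 0.5 = 9.72 | 1, 11 | 0.767 | 0.810 |

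Each gives 12 as the smallest N, and each f lies in the stated range. The result depends on alpha: at 0.01 the 3x3 interaction at f = 0.25 needs 17.

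**3. What the HIIT/MICT x time (2x3) interaction could detect.** Six cells, df 2 and 2(N - 1), 80% power, same assumptions. Solve for f = sqrt(lambda x 0.5 / (6N)).

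- N = 12: lambda needed 11.08, so f = sqrt(11.08 x 0.5 / 72) = 0.277.
- N = 14: lambda needed 10.84, so f = sqrt(10.84 x 0.5 / 84) = 0.254.

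**4. Loss allowance.**

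- Expected completers: 14 x 0.82 = 11.48, below 12.
- Enrolment needed to keep 12: 12 / 0.82 = 14.63, so 15, or 16 with equal numbers of men and women.
- Fourteen can lose two (2/14 = 14.3%). A third loss (3/14 = 21.4%) leaves 11.
- If losses are independent at 18%, the chance that at least 12 of 14 complete is 0.53.

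**5. Samples.** One CON draw: 14 x (3 + 3 + 1) = 98. Three CON draws: 14 x 9 = 126. Difference: 28.

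**The case against.** The best defence is that the single-draw sentence is a slip. The Visit 3-5 text and sections 3.2, 3.2a and 5.2 all point to three CON samples. That may well be so, but the Metabolomics paragraph is the one that staff would follow for blood sampling, and nothing in the documents says which text governs. The conflict stands either way.

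A second defence is that the loss shortfall is about half a participant. That is right, and it is why this is the minor part.

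Third, every power figure here assumes sphericity. That stands as a limit: on a simple calculation with epsilon 0.75, the 3x3 power at 12 falls from 0.81 to about 0.71.

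A reader might also go further than the documents allow:

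- *That N=12 rests on the CON draws.* Section 5.1 names no test, takes its effect sizes from HIIT vs MICT, and yields 12 by a two-level comparison of those regimens as well.
- *That a single draw leaves the trial underpowered.* Carrying f = 0.25 over to the 2x3 interaction would require 15 completers. But an f defined on nine cells does not transfer to six without knowing the response pattern and how the source defined f.
- *That the single draw explains the lack of hormone samples during sessions, which Aim 2 mentions.* Section 4.1 schedules no draw during exercise under any regimen.

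**Conclusion.** The point holds. The single CON draw in section 4.1 is incompatible with the 3x3 ANOVA on metabolites and hormones, with the blood-marker part of Aim 1, and with CON in two of the three regimen x sex ANOVAs. The loss is two cells of nine and two of four interaction degrees of freedom, whatever the timing of the draw. It would be too strong to say that every post-baseline comparison with CON disappears: that is so only if the draw is on arrival, which is not stated. Indirect calorimetry, glucose monitoring and the within-regimen paired tests do not depend on it.

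The 18% allowance in section 5.1 is wrong as written but small: 11.5 expected completers against 12. If the 12 came from the 3x3 interaction at f = 0.25, alpha 0.05 and sphericity, power with 11 completers is 0.76. On any other basis that figure does not apply. None of this shows that 14 is an inadequate sample.

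**What to change.** Before CON sampling, reconcile the Metabolomics paragraph of section 4.1 with the Study Summary, sections 2, 3.2, 3.2a and 5.2, and the Visit 3-5 text.

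- *If three CON draws apply:* correct section 4.1. Cost: up to 28 more plasma samples (98 to 126) if these were not budgeted.
- *If the single draw stands:* state when it is taken and replace the blood-marker 3x3 ANOVA with a HIIT/MICT x time (2x3) analysis. Limit the blood-marker parts of Aims 1 and 2 to HIIT vs MICT, and likewise the regimen x sex ANOVAs at the times with no CON sample (the post-exercise times, if the draw is on arrival). Report the minimum detectable 2x3 interaction f for 80% power: about 0.28 at 12 completers and 0.25 at 14, with the assumptions stated. Cost: no extra samples, but change at rest is given up for these markers.

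In section 5.1, keep 14. Say either that it tolerates two losses (14.3%), or that at 18% about 11 are expected to complete, and restate the power for that number. If 18% is still the expected loss, the second is the fuller disclosure. Name the test, alpha and effect size behind N=12. This costs wording only, with no added participants.

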5.2 Statistical Methods

For aim 1, changes in the first principal component, as well as any additional components for which the associated eigenvalue is greater than one, will be evaluated using paired t-tests at the 2-sided 0.05 level. Changes in individual metabolic intermediates will be evaluated using paired t-tests at the 2-sided 0.01 level. Differences in metabolomics and counterregulatory hormones markers between treatment regimens will be evaluated using two-way ANOVAs [regimen (HIIT vs. MICT vs. CON) \times time (base vs. immediate post vs. 1h post)]. Exploratory analysis of the modulatory effects of sex on metabolomics markers will be evaluated using separate regimen-by-sex mixed factorial ANOVAs [regimen \times sex], at each time point.

For aim 2, CGM data will be evaluated as previously recommended; data will be aggregated over the 24hrs; area under the curve data will be compared across trials.(25) Counter-regulatory hormones will be evaluated using a two-way mixed factorial ANOVA. Activity data will be captured to potentially be used as a covariate when collating CGM data.

For aim 3, spearman correlations will be completed to understand associations between metabolomics outcomes and physiological variables (i.e. body fat, lean mass, visceral fat).

6 Safety and Adverse Events

Risks associated with participating in this study are **possible**. In-test monitoring by the research team, who are certified fitness professionals trained in CPR/AED, are in place to ensure the safety of all subjects. Personnel trained in phlebotomy and with radiation exposure training will complete the blood draws and DXA scans, respectively.

In accordance with the Exercise and Sport Science Institutional Review Board Standard Operating Procedures (EXSS-IRB SOP), 3 trained research personnel (for safety purposes per IRB procedures) will perform cardiorespiratory fitness testing. Other precautions include: licensed medical professional (MD, ATC) on call, operational AED, and a land line within 10 feet of the testing in order to make emergency call, if required. Additionally, the lab is located within 500 feet of the University Athletic Training facility. If a cardiovascular event does occur, 911 will be called; UNC Hospitals and Emergency room are in very close proximity to the lab.

The risk for any exchange of blood borne pathogens is low. All blood samples will be handled by individuals with blood borne pathogen and laboratory safety training. These procedures follow the rules of universal precautions, and all investigators and research assistants have up to date training. Continuous glucose monitoring (CGM) procedure is routinely used in clinical practice. The main risks of CGM are local irritation from the sensor or tape.

Available evidence suggests HIIT provides similar or superior improvements in cardiorespiratory fitness and endothelial function compared to moderate intensity exercise, without a detrimental decline in blood glucose.(18, 19) However, hypo- or hyperglycemic events are a risk. Study personnel will be trained to identify the signs and symptoms of a blood glucose level that is low or high. They will also be trained to check the blood glucose level, using a glucometer. If low blood glucose occurs during a study visit (< 70 mg/dL), study personnel will be trained to administer 15 grams of an oral carbohydrate, and to repeat as needed every 10 minutes until the blood glucose level is > 70 mg/dL. If the blood glucose level is above 300 mg/dL during a study visit, study personnel will be trained to check for urinary ketones. After the exercise session, subjects will be instructed to take their usual dose of insulin or other diabetes medication as prescribed. If participants experience hypoglycemia or hyperglycemia outside of study visits, they will be advised to treat these situations per their usual diabetes care plan.

Potential adverse events will be reviewed at each visit with each subject, and will be recorded within the subject data collection folder. Adverse events in aggregate will be reviewed by the study team and the nature of adverse events that

would trigger reconsideration of the protocol would be highlighted. If it is clearly found that an adverse event is related to supplements, it will be immediately reported to the sponsor and the IRB and the correspondence will be negotiated.

The 2017 DAIDS Therapeutic Research Program's guide for grading AEs/SAEs during clinical trials will be used to evaluate the severity of the event, and will be categorized as: Grade 1 (mild), Grade 2 (moderate), Grade 3 (severe), Grade 4 (Potentially life-threatening), Grade 5 (death).

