3.2 Primary Study Outcomes

The primary study outcomes include circulating metabolites that will be measured using an untargeted mass spectrometry-based platform with fasting concentrations of up to 1500 endogenous metabolites related to mitochondrial function, fatty acid oxidation, insulin resistance, and glucose regulation. Targeted metabolomics analysis for acylcarnitines and amino acids will be completed; non-targeted analyses will also be performed as an exploratory analysis, in order to promote the identification of unknown metabolites in addition to the known biology and physiology. Responses will be collected prior to, immediately post, and 1 hr post exercise.

3.2a. Secondary Study Outcomes

Counterregulatory hormones (cortisol, lactate, glucagon) will be evaluated at the same time points. Glucose will be continuously monitored for 48 h post exercise. , and glycemic control through 48 hrs after HIIT, compared to MICT versus a no exercise CON.

3.2b. Tertiary Study Outcomes

Tertiary outcomes will evaluate the influence of biological sex and physiological outcomes (i.e. body composition, lean mass, visceral fat) on the metabolomics profile of these subjects.

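### Section 5.2's eigenvalue-above-one rule does not select principal components at this sample size, and the matrix to be decomposed is not defined, so many noise components may each be tested at 0.05

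*Combined protocol and SAP*

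**What the plan says.** The Study Summary assigns "Principal Component Analysis for metabolomics data" to Aim 1. Section 5.2 gives the detail. The components to be tested are "changes in the first principal component, as well as any additional components for which the associated eigenvalue is greater than one". Every one of them gets its own paired t-test, two-sided, at 0.05. The same section adds a second layer ("Changes in individual metabolic intermediates will be evaluated using paired t-tests at the 2-sided 0.01 level") and a third ("Differences in metabolomics and counterregulatory hormones markers between treatment regimens will be evaluated using two-way ANOVAs").

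Section 3.2 makes circulating metabolites the primary outcome, with "fasting concentrations of up to 1500 endogenous metabolites" from the untargeted platform. It labels the non-targeted analysis exploratory and does not give the size of the targeted acylcarnitine and amino acid panel.

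Four things are not stated anywhere: whether the PCA is fitted to pooled levels, baseline levels or change scores; whether the data are transformed or scaled; whether each participant's own level is removed; and which pair the paired t-test compares (before and after exercise, or HIIT and MICT).

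**The concern.** The eigenvalue-above-one rule is the only device in the plan that limits how many components are tested. It compares each eigenvalue with the average eigenvalue of a correlation matrix, which is 1. When there are about as many metabolites as samples, sampling error alone spreads the eigenvalues widely around 1, and a large fraction lie above it. When metabolites far outnumber samples, the whole variance falls on a few non-zero eigenvalues and all of them exceed 1. The list of tested components is then set by the dimensions of the data and not by its structure.

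A second issue is conditional. A cross-over asks about variation within a person. An ordinary PCA of pooled levels follows whatever variance is largest, including stable differences between people. Taking changes in the score afterwards removes each person's level, but the direction of the component is already fixed.

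At stake is how the multivariate test of the primary outcome can be read. A significant late component may be noise, and a null on component 1 may say little about HIIT against MICT.

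**Working it through.** **Inputs.** 14 participants (Section 5.1). Three blood samples at each of the HIIT and MICT visits and one at CON (Section 4.1, metabolomics paragraph), so 14 × 2 × 3 = 84 exercise-visit samples, or 14 × 7 = 98 with CON. Up to 1500 metabolites (Section 3.2). The targeted panel of 60 is an assumption. The plan gives no expected number of components, so there is no figure of its own to reproduce here.

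**Step 1: what the rule does to noise.** On the correlation scale the eigenvalues of p metabolites sum to p. With n samples, at most min(n − 1, p) of them are non-zero. The average non-zero eigenvalue is therefore:

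- 84 × 1500: 1500/83 = 18.1
- 14 change scores × 60: 60/13 = 4.6
- 84 × 60: 60/60 = 1

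In the first two cases a threshold of 1 lies far below the average. In the third it sits at the average. Simulated independent standard-normal data give:

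| Samples × metabolites | Components available | Kept by eigenvalue > 1 |
|---|---|---|
| 84 × 60 | 60 | about 25 |
| 84 × 1500 | 83 | 83 |
| 98 × 1500 | 97 | 97 |
| 28 change scores × 60 | 27 | about 20 |
| 14 change scores × 60 | 13 | 13 |

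These counts need no assumption about effect size or covariance. Person-centring does not cure them: centred noise at 84 × 60 still keeps about 24.

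**Step 2: consequence for the tests.** Each kept component is tested at 0.05, so noise alone gives an expected 25 × 0.05 = 1.25 significant components per contrast at 84 × 60, and 83 × 0.05 = 4.15 at 84 × 1500. In structured simulations (12 people, 7 samples each, 60 metabolites, pooled levels, no true HIIT-MICT difference), about 9 to 12 components were tested and at least one was significant in 35-37% of runs.

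**Step 3: parallel analysis instead.** A component is kept only if its eigenvalue exceeds the 95th percentile from permuted data. On pure noise this kept any component in 3 of 100 runs at 84 × 60 and 2 of 100 at 14 × 60. In a structured setting with no HIIT-MICT difference, the components tested fell from about 12 to at most 8, and the chance of any false signal fell from 39-45% to 21-29%.

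**Step 4: can component 1 point at people?** Section 5.1 assumes a "conservative correlation of 0.5 between repeated outcomes". Under compound symmetry this puts half of the *residual* variance between people. Total variance also contains the condition effect, so the between-person share is 0.5/(1 + f²). Over the plan's F range that is 0.5/1.0625 = 47% at 0.25 and 0.5/1.9801 = 25% at 0.99.

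This share does not fix component 1. With the correlation held at 0.5, the between-person part of component 1 ran from about 4% to 93% across assumed covariance structures.

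Detection of a true HIIT-MICT difference by component 1, with 60 metabolites throughout:

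| Assumed setting | Pooled levels | Person-centred |
|---|---|---|
| 14 people, 30% responding, HIIT response 1.5 × MICT, 1 or 3 between-person factors | 3-13% | 48-96% |
| 12 people, 30% responding, 0.8 SD time effect and 0.8 SD difference | 12% | 9% |
| 12 people, 30% responding, 1.5/1.5 SD, different between- and within-person loadings | 54% | 47% |
| 12 people, 30% responding, 1.5/1.5 SD, same loadings | 12% | 51% |
| 12 people, 80% responding, 0.8/0.8 SD | 70% | 98% |
| 12 people, effect along a within-person factor, 0.8/0.8 SD | 94% | 95% |

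The first row holds only under its own assumptions. Between-person variance is also not the only cause of low power. At correlation 0.2, component 1 was only 17% between-person and still had 6% power.

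**The case against.** The strongest objection is to a broader claim that a reader might infer: that the plan's components are built from total variance, half of it between people by the plan's own 0.5, so component 1 mainly describes who the participants are and the Aim 1 test is aimed at the wrong variance. The documents do not support that. They never state the PCA input, and a PCA of change scores fits the wording and contains no stable person level. The 0.5 is a power-calculation input, not a variance component of the metabolite panel. Section 5.2 does not name HIIT against MICT as the component contrast, and it assigns regimen differences to the two-way ANOVAs. Further components, single-metabolite tests and ANOVAs are also planned, so a null on component 1 would not settle Aim 1. All of this stands, and it limits the second issue to a possibility.

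It can also be said that the later components rescue the analysis: in the pooled-level simulations of a true difference, at least one retained component detected it in 90-100% of runs. That does not help much when 35-37% of runs with no difference also produced a significant component.

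The 1500-metabolite count belongs to analysis that Section 3.2 calls exploratory. That is fair, but the rule also fails with 60 metabolites, and fails completely with 14 change scores.

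Multilevel PCA is one reasonable choice among several. That stands too. What the plan needs is a stated input and a retention rule that can reject noise.

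**Conclusion.** The concern holds in two parts of unequal strength.

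The firm part is that eigenvalue above one does not select components here. Noise keeps about 25 of 60, 83 of 83 or 13 of 13, depending on the matrix, and each kept component is tested at 0.05. This rests only on the sample count, a correlation-scale PCA and, for the targeted panel, an assumed size near 60.

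The conditional part is that, if pooled uncentred levels are used, component 1 can follow between-person differences and miss a HIIT-MICT difference. Simulated component-1 power ranged from about 5% to 100% with structure that the documents do not give. It would be wrong to present any single figure, such as 3-13%, as a property of this plan, or to derive the problem from the 0.5 planning correlation.

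The change should be made before analysis. It is not a reason to doubt the trial's design.

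**What to change.** In Section 5.2:

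1. State which metabolite set enters the PCA. Log-transform and scale each metabolite, then subtract each participant's own mean over their samples. Fit the PCA to these within-person data.
2. Replace eigenvalue above one with parallel analysis: retain components whose eigenvalue exceeds the 95th percentile from permuted data. Fix the number of permutations and the seed in advance.
3. Score every sample on those fixed loadings. Name the HIIT-MICT difference in change from baseline as the component contrast, and say at which time point or points.
4. Describe between-person components separately under Aim 3.

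The cost is a few sentences and a few lines of code, with no change to data collection. Fewer components will be tested, and between-person structure leaves the primary PCA. Centring will not raise component-1 power in every setting. Parallel analysis lowers the chance of a false signal but does not bring it to 5% (21-29% remained in the setting above), so any claim across several retained components still needs its own multiplicity statement.
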